5.4 BLINDING ASSESSMENT

Subjects and the study clinician performing efficacy assessments will remain blinded to the assigned treatment group for the duration of the study. Blinding will be assessed through completion of blinding questionnaires completed by both the subject and the blinded clinician at study end.

5.5 FOLLOW-UP

Subjects will be asked to return to the clinic for follow-up visits at 90, 180 and 365 days post-treatment.

At all visits, subjects will be assessed for safety and efficacy, standardized images will be taken (refer to Ulthera's study specific photography guidelines and procedures document), adverse events and protocol deviations will be assessed.

At the 90-day follow-up appointment in addition to the above referenced assessments, the subject will complete a Patient Satisfaction Questionnaire. An additional pregnancy test, if applicable, will be completed at the 365-day follow up visit.

5.6 PROTOCOL DEVIATIONS

This study should be conducted as described in this protocol, except for an emergency situation in which the protection, safety, and well-being of a subject requires a protocol deviation, based on the judgment of the investigator (or a responsible, appropriately trained professional designated by the investigator). If the deviation from the protocol is necessary to protect the physical well-being of a subject in an emergency, such protocol deviations must be reported to the Sponsor and the reviewing IRB as soon as possible, but no later than five working days after the emergency occurred.

Any occurrence of pregnancy during the course of the trial must be reported to the Sponsor and documented as a protocol deviation.

In the event of a significant deviation from the protocol due to an accident or mistake, the investigator or designee must contact the Sponsor at the earliest possible time by telephone to discuss the deviation and its impact on the study and subject continuation in the study. These discussions will be documented by the investigator and the Sponsor, and reviewed by the monitor.

5.7 WITHDRAWAL CRITERIA AND PROCEDURES

All subjects have the right to withdraw at any point during the study without prejudice. The investigator can discontinue any subject, at any time, if medically necessary. The reason for subject's withdrawal should be documented on the appropriate study-specific data form. The subject must undergo the recommended follow-up assessments specified for the last study visit unless contraindicated due to a medical condition. Withdrawn subjects will not be replaced.

5.8 END OF STUDY (COMPLETION)

All subjects who have signed an Informed Consent Form, except for screen failures, will be considered enrolled in the study. Subjects who complete the study duration will be considered to have completed the study. Any subject who does not return for a scheduled follow-up visit will be contacted at least twice by telephone to determine the cause for the missed visit and to try to get the subject scheduled for the follow-up. A new visit will be scheduled as soon as possible. All subjects should be followed until completing the study follow-up or until study discontinuation (withdrawal) for other reasons. The reason for study discontinuation should be documented for each subject. Subjects will be deemed "Lost-to-Follow-up" if they have not returned within six weeks after the last follow-up target. For any subject lost to follow-up at least three attempts to contact the subject must be documented; the attempts must be two phone calls/emails and a registered letter.

6. STATISTICAL ANALYSIS

6.1 STUDY OBJECTIVE

The objective of this study is to demonstrate that the safety and efficacy of Simulines transducers at Energy Level 2 [EL2] is not inferior to treatment with Standard transducers at Energy Level 2 [EL2] in order to limit the energy level of both types of transducers to a maximum of EL2 for lift indications. To fulfill this objective we will be using the same treatment depths and regions treated as those used in the pivotal study that supported the submental/neck clearance, but at EL2 instead of Energy Level 4 [EL4]. Simulines transducers deliver 2 lines of treatment per pulse (push of the button) versus Standard transducers which deliver 1 line of treatment per pulse.

6.2 DETERMINATION OF SAMPLE SIZE AND STUDY SUCCESS

A sample size of 260 randomized subjects will be required to account for up to 16% attrition to have 80% power to determine non-inferiority given a response rate of 73% in both randomized groups and a non-inferiority margin of 15%. Response is defined as greater than 20 mm² reduction in neck and submental area from baseline. The study was powered based on the expected response rate of 73% as seen in the pivotal trial supporting the neck/submental lift indication FDA clearance K121700. The observed response rate of the prior pivotal trial (73%) was higher than the minimum response rate required (65%) for success of the supporting trial. Study success will be achieved given a statistically significant determination for non-inferiority for the primary efficacy objective. Statistical significance is determined using a one-sided $\alpha=0.05$.

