	
 ii. Obtain Global Aesthetic Improvement Scale (CGAIS and SGAIS). c. 365±30 days 
 i. Obtain images (2D photographs, 5 views; 3D photographs with Quantificare imaging system at applicable site(s)); ii. Obtain Global Aesthetic Improvement Scale (CGAIS and SGAIS); and iii. Obtain pregnancy screen (if applicable). iv. Obtain blinding assessments: Clinician and Subject Blinding Questionnaires. 6. Follow-up Visits for safety evaluation: 
 a. Immediately post-treatment 
 i. Assess for adverse events. b. All follow-up visits 
 i. Assess for adverse events.

Primary Endpoint:
	
1. Efficacy will be assessed based on quantitative measurements of neck and submental lift at 90 days post-treatment compared to baseline. Subject response is defined as ≥ 20 mm² reduction in 2D submental area from baseline. (Note: this is the same methodology and success criteria which supported the FDA clearance of the submental/neck lift indication for this device, Attachment A.) Simulines transducers will be considered non-inferior to Standard transducers using a non-inferiority margin of 15% between the two arms of the trial. The study was powered based on the expected response rate of 73% as seen in the pivotal trial supporting the neck/submental lift indication FDA clearance K121700. The observed response rate of the prior pivotal trial (73%) was higher than the minimum response rate required (65%) for success of the supporting trial.

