Energy Level is the total energy output for a line of TCPs expressed in Joules (J). The number of Joules is determined by the Acoustic Power in Watts (W) and the length of time (T, in seconds) the power is on/being delivered to create an entire line of TCPs. The equation to determine the energy level (EL) for a TCP in Joules is $W \times T = J$. The Ulthera system has capability of 4 different energy levels to be used commercially. The desire is to limit the lift indications to the lower two energy levels for patient comfort. When using the Ulthera System, clinicians will continue to have the ability to adjust the energy settings between two pre-set energy levels programmed for each transducer based on their clinical judgement for the treatment being delivered. Energy Level 2, EL2, (shown in Table 1.4-1) will be used in this study. Other energy levels will not be allowed in this trial. The stated default energy is the total energy delivered to the patient to form a singular TCP when using the standard transducers. The total energy stated for the Simulines transducer is the total energy delivered to the patient to form two TCPs. As such, each TCP created using the Simulines transducer receives half of the stated energy per TCP. Simulines transducers exploit a particular method of constructive acoustic interference to achieve two simultaneous locations of peak spatial intensity, thereby creating two TCPs at the same depth, at once.

In the case of the DS 4-3.0S,

Each treatment region is treated in a lined pattern ("line" is a row of TCPs). Using the Standard transducer, multiple lines of treatment are delivered as the transducer is advanced 2-3 mm within the region, and multiple passes of the region are utilized until all treatment lines have been delivered for that region, and treatment of the region is complete.

Because the Simulines transducer is delivering two simultaneous lines, the transducer must be advanced twice as far (4-6mm). This distance between energy deliveries is called the walk distance. Multiple passes of this wider walk distance are utilized until all lines are delivered within a region. The user then moves to the next region of treatment. Treatment patterns under the current protocol are described in Section 5.1.

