The quantitative assessment for the right and left side of the face yielded a response rate of 72.9% (*51 out of 70*) of subjects that had a visible tissue lift of ≥ 20.0 mm² of the submental area when comparing the pre-treatment and 90-day post-treatment photos. The average area of tissue lift in the study subjects who were considered responders were 71.97 mm² and 71.69 mm² for their left and right sides, respectively. The quantitative results were consistent for both the right and left side of the face. Additionally, 84.3% of subjects who were identified as responders by quantitative assessment were also identified as responders in the qualitative masked assessment. Based on the masked assessment conducted by three experienced clinicians of pre- and 90-day post-treatment photograph pairs, 68.6% of subjects had improvement (*visibly observable tissue lift*) in the submental area (*beneath the chin*) and neck. The patient satisfaction questionnaire indicated that 67% of the subjects saw an improvement in face and neck characteristics.

This study demonstrated that Ultherapy[®] is safe and efficacious for the improvement in submental (*beneath the chin*) and neck laxity and supported FDA clearance of the submental/neck lift indication the device received. The efficacy of the treatment using EL2 energy levels is expected to produce a similar 72.9% response rate.

1.6.4 PROSPECTIVE, MULTI-CENTER, PIVOTAL TRIAL EVALUATING THE SAFETY AND EFFECTIVENESS OF THE ULTHERA SYSTEM FOR IMPROVEMENT IN LINES AND WRINKLES OF THE DÉCOLLETÉ

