2. STUDY OBJECTIVE AND DESIGN

2.1 STUDY OBJECTIVE

The objective of this study is to demonstrate that the safety and efficacy of Simulines transducers at Energy Level 2 [EL2] is not inferior to treatment with Standard transducers at Energy Level 2 [EL2] in order to limit the energy level of both types of transducers to a maximum of EL2 for lift indications. To fulfill this objective we will be using the same treatment depths and regions treated as those used in the pivotal study that supported the submental/neck clearance, but at EL2 instead of Energy Level 4 [EL4]. Simulines transducers deliver 2 lines of treatment per pulse (push of the button) versus Standard transducers which deliver 1 line of treatment per pulse.

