5.3.1 PRIMARY ENDPOINT

Efficacy will be assessed based on quantitative measurements of neck and submental lift at 90 days post-treatment compared to baseline. Subject response is defined as ≥ 20 mm² reduction in 2D submental area from baseline.

(Note: this is the same methodology and success criteria which supported the FDA clearance of the submental/neck lift indication for this device). Simulines transducers will be considered non-inferior to Standard transducers using a non-inferiority margin of 15% between the two study arms. The study was powered based on the expected response rate of 73% as seen in the pivotal trial supporting the neck/submental lift indication FDA clearance K121700. The observed response rate of the prior pivotal trial (73%) was higher than the minimum response rate required (65%) for success of the supporting trial.

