6.4.3 EFFICACY ANALYSIS

6.4.3.1 PRIMARY EFFICACY ANALYSES

Subjects included in the analysis: All ITT subjects will be included in the analysis.

Endpoint: Subject response is defined as ≥ 20 mm² reduction in 2D submental area from baseline. The left and right side value at baseline will be averaged to result in the 2D submental area at baseline. The left and right side value at 90 days will be averaged to result in the 2D submental area at 90 days. In the event, only either the left or right side data is available, it will be used. Response will be calculated as baseline – 90 days. The evaluator that determines 2D submental area is blinded to follow-up and study group.

Hypothesis:

H₀: The proportion of responders at 90 days as compared to baseline for the test group is inferior as compared to the control group given a non-inferiority margin of δ , $p_{\text{control}} - p_{\text{test}} \geq \delta = 15\%$.

H_a: The proportion of responders at 90 days as compared to baseline for the test group is not inferior as compared to the control group given a non-inferiority margin of δ , $p_{\text{control}} - p_{\text{test}} < \delta = 15\%$

Sample Size Rationale: The sample size calculation assumes 73% response in both randomized groups. Power was set at 80%, one-sided Type I error controlled at 5%, a non-inferiority margin of 15% and PASS 12 Non-inferiority for two independent proportions using the Z-test with unpooled variance was used. The sample size requires 109 subjects per randomized group to have data necessary to calculate the primary endpoint. The total sample size of 218 was corrected for up to 16% attrition to arrive at 260 subjects randomized in the study.

Primary Statistical Analysis: The primary statistical analysis will be conducted using the observed data in the intent-to-treat patients using the Z-test (unpooled) for two independent proportions. Statistical significance is determined using a one-sided $\alpha=0.05$.

Additional Statistical Analysis: If there are intent to treat subjects with missing data, the analysis as specified in Section 6.4.1 Handling of Missing data will be conducted. The analysis in Section 6.4.1 regarding pooling will be conducted as specified in that section. The analysis will be completed for the subset of per protocol patients.

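### Does the success rule need an absolute response criterion because both arms are treated at EL2?

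*Combined protocol and SAP*

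**What the plan says.** Section 6.2 gives one condition for success: "Study success will be achieved given a statistically significant determination for non-inferiority for the primary efficacy objective". Section 6.4.3.1 tests the control rate minus the test rate against 15 percentage points at one-sided 5%, as follows: "The primary statistical analysis will be conducted using the observed data in the intent-to-treat patients using the Z-test (unpooled) for two independent proportions".

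Both arms are at EL2. Section 6.1 explains that the comparison is made "in order to limit the energy level of both types of transducers to a maximum of EL2 for lift indications", and Section 1.4 gives the reason: "The desire is to limit the lift indications to the lower two energy levels for patient comfort". Section 1.6.3 reports 51 of 70 responders (72.9%) in a single-arm, 290-line study and adds: "The efficacy of the treatment using EL2 energy levels is expected to produce a similar 72.9% response rate". The objective places the clearance study at EL4.

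Section 5.3.1 and the synopsis define a responder by a 20 mm² reduction and then remark in parentheses that "this is the same methodology and success criteria which supported the FDA clearance of the submental/neck lift indication for this device". They next state the 15% margin. They close by saying that the earlier trial's observed 73% "was higher than the minimum response rate required (65%) for success of the supporting trial".

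Section 6.4.1 plans a summary of the primary endpoint by randomised group and by site. Section 6 specifies no confidence interval for the rate within each arm.

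**The concern.** The purpose in Section 6.1 is to cap both transducer types at EL2. That depends on EL2 producing a useful response as well as on Simulines matching Standard. There is no EL4 arm and no untreated arm, so the test cannot speak to the first part. The visible text gives no clinical response rate for Standard transducers at EL2. It offers only an expectation carried over from a study at a higher energy level and a different line count (290, against at least 672 single-line pulses in the Standard arm here).

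If both arms responded poorly but similarly, the trial would still be declared a success, and how to read the low rates would be settled after the data were seen.

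The parenthesis in Section 5.3.1 adds to the unease. If the shared success criteria included the earlier 65% minimum, success would mean something different there from what Section 6.2 says.

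**Working it through.** **Inputs.** Section 6.4.3.1 gives 73% in both arms, a margin of 0.15, one-sided α of 0.05, 80% power, an unpooled Z-test, 109 evaluable per arm, 16% attrition and 260 randomised. Section 1.6.3 gives 51/70. Sections 5.3.1 and 6.2 give 65%. True rates other than 73% are illustrative.

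**1. The plan's own figure.**

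n per arm = (1.645 + 0.842)² × 2 × 0.73 × 0.27 / 0.15² = 108.3, rounded up to 109. The total is 218, and 218 / 0.84 = 259.5, so 260. Both figures reproduce.

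**2. Chance of passing when the two arms have the same true rate.** This is exact binomial enumeration of the rule (0.15 − d) / SE > 1.645, where d is the observed control rate minus the test rate and SE is unpooled.

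| Common true rate | 109 per arm | 130 per arm |
|---|---|---|
| 73% | 0.805 | 0.860 |
| 65% | 0.747 | 0.813 |
| 55% | 0.730 | 0.791 |
| 50% | 0.729 | 0.790 |

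The variance p(1 − p) is largest at 50%, so the chance of passing is lowest there and rises again below it (0.872 at 20% with 109 per arm). The rule is nearly blind to the common rate.

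**3. Two results that both pass.**

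- Control 80/109, test 79/109: d = 0.009, SE = 0.0602, one-sided 95% upper limit 0.009 + 1.645 × 0.0602 = 0.108.
- Control 60/109, test 60/109: d = 0, SE = 0.0674, upper limit 1.645 × 0.0674 = 0.111.

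Both limits are below 0.15. The planned summary by group would nevertheless show about 73% in the first case and 55% in the second. The combined 95% Wilson intervals, computable from the reported counts, are 66.7% to 78.4% (159/218) and 48.4% to 61.5% (120/218). The two cases can be told apart with what the plan already reports.

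**4. What a reading against 65% would do.** The earlier 51/70 has a Wilson interval of 61.5% to 81.9%, which includes 65%. The protocol sets that trial's observed rate against 65% and does not show that an interval had to exclude it. Suppose an interval covering 65% were called inconclusive. With 218 combined, the interval covers 65% whenever there are 128 to 155 responders:

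| True rate | Probability that the combined interval includes 65% |
|---|---|
| 60% | 0.68 |
| 62% | 0.86 |
| 65% | 0.95 |
| 68% | 0.85 |
| 70% | 0.66 |
| 73% | 0.29 |

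For a single arm of 109 at a true 73%, the probability is 0.57.

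**5. The parenthesis.** It directly follows the 20 mm² responder definition. In the synopsis it points to Attachment A, which the table of contents lists as quantitative methodology. The next sentence states this trial's own rule, the 15% margin, and the 65% is assigned to the supporting trial. Section 6.2, whose heading names study success, gives one rule only. The natural reading is that the responder definition is what is shared.

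**The case for a change.** The strongest case for a change is that the protocol attaches to this comparison a purpose, the EL2 cap, that a relative test alone cannot support. Saying in advance how the absolute rates will be read costs only a few sentences and three intervals, and is credible only if written before unblinding. Section 6.4.3.2 calls the secondary endpoints supportive, so they do not fill the gap formally.

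The facts in this stand: the rule is relative, the purpose is wider, and no interval is specified. Stating the intervals and clarifying the parenthesis would be harmless. But neither alters the test, the sample size or the decision, and the counts needed are already to be reported by group.

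Anything that did alter the reading would need a benchmark. The only candidate, 65%, belongs to a study at another energy level with fewer lines. An interval rule against it would be stricter than the comparison the protocol describes. Nor would such a rule isolate EL2 efficacy, because a before-and-after rate without an untreated or EL4 arm cannot do that.

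**Conclusion.** No change is needed. Followed as written, the plan reaches a sound conclusion on the question it tests: whether Simulines at EL2 is within 15 points of Standard at EL2. The near-constant chance of passing (0.805 at 73%, 0.729 at 50%, 109 per arm) is ordinary for a fixed margin. It would mislead only if a pass were presented as proof of EL2 efficacy, and no section does that. The missing interval is detail that an analyst would supply from the Day-90 counts by group. The parenthesis is loose wording with one likely meaning.

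This rests on two assumptions. The first is that the Day-90 rates are reported by arm as Section 6.4.1 says. The second is that the shared success criteria mean the 20 mm² definition, which cannot be confirmed because Attachment A is not in the supplied text. Much of the Simulines testing section (1.7.2) is redacted and may hold EL2 data, so the EL2 expectation cannot be called unsupported.

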6.3 ANALYSIS POPULATIONS

The intent-to-treat population is defined as all subjects who were randomized with study group defined by the randomization.

The per-protocol population is defined as the subset of ITT subjects who:

- met the major inclusion and exclusion criteria
- received within +/- 5% of the total lines per protocol for the randomized treatment
- had in-office follow-up visits either in window or out of window but within 7 days of window open/close
- had primary endpoint data available with acceptable photographic quality as determined by the 3rd party evaluator
- did not have any major protocol violations

The major inclusion/exclusion criteria include age 30 to 70 years, inclusion #3, #4, #8, adherence to photography procedures (i.e., removal of jewelry and makeup), exclusion #1, #7, #8, #11 - #15, #19, #21, #24, #27-#29.

The major protocol violations are defined as:

- use of any other pre-medication for pain besides ibuprofen and administration of ibuprofen less than 45 minutes or more than 135 minutes prior to initiation of study treatment
- any change to the energy level of the device during treatment
- accidental unblinding of investigators completing blinded assessments or subjects during treatment

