6.4.3.2 SECONDARY EFFICACY ANALYSES

The secondary efficacy analyses will be performed using subjects in the intent to treat population who have a non-missing assessment for the efficacy parameter at the time point being analyzed. The secondary endpoints are supportive in nature and are evaluated to provide additional information and are not intended to support additional claims. Descriptive statistics may be included in the labelling and for this purpose are defined as number of observations, mean, standard deviation, median, minimum and maximum for continuous variables and number and proportion of observations for categorical variables. The secondary outcomes may additionally be completed for the subset of per protocol patients.

Secondary efficacy outcomes will be:

6.4.3.2.1 Quantitative improvement measurements of submandibular and submental lift at 180 and 365 days post-treatment compared to baseline.

Endpoint: Subject response is defined as $\geq 20 \text{ mm}^2$ reduction in 2D submental area from baseline. The left and right side value at baseline will be averaged to result in the 2D submental area at baseline. The left and right side value at 180 days will be averaged to result in the 2D submental area at 180 days. Similarly, at 365 days. In the event, only either the left or right side data is available, it will be used. Response will be calculated as baseline – follow-up. The evaluator that determines 2D submental area is blinded to follow-up and study group.

Statistical Analysis: A repeated measures model will be used to analyze the data from this objective. The dependent variable will be response (y/n). The independent variables will be study group and day of follow-up. A covariance structure will be used to account for the correlation expected among the repeated observations collected for each subject. The covariance structure that fits the data best, i.e. results in the lowest Schwarz Bayesian Information Criteria (BIC) value all else held constant will be used, among the

unstructured, compound symmetric or auto-regressive types. Statistical significance will be determined using a two-sided $\alpha=0.05$.

6.4.3.2.2 Comparison of improvement in overall lifting and tightening of skin as determined by a masked, qualitative assessment of photographs at 90, 180 and 365 days post-treatment compared to baseline.

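### The per-protocol visit rule in Section 6.3 names no visit, so read literally it can remove a subject with a valid Day-90 result from the supportive Day-90 analysis because of a later visit

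*Combined protocol and SAP*

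**What the plan says.** Section 6.3 defines a single per-protocol population through a list of conditions that must all hold. One concerns visit timing: the subject "had in-office follow-up visits either in window or out of window but within 7 days of window open/close". A separate one concerns the measurement itself: the subject "had primary endpoint data available with acceptable photographic quality as determined by the 3rd party evaluator".

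Section 5.5 identifies the clinic visits: "Subjects will be asked to return to the clinic for follow-up visits at 90, 180 and 365 days post-treatment". The contacts at Days 3 and 7 are by telephone (synopsis, Treatment Outline), so they are not in-office visits. The windows in the synopsis and Table 3.1-1 are 90±14, 180±21 and 365±30 days.

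The primary endpoint is measured at Day 90 (Section 6.4.3.1): "Response will be calculated as baseline – 90 days". The primary analysis uses observed data in the ITT subjects. The per-protocol set comes in under additional analyses in the same section: "The analysis will be completed for the subset of per protocol patients". Section 6.4.3.2 makes the same set optional elsewhere: "The secondary outcomes may additionally be completed for the subset of per protocol patients". No section limits the visit condition to Day 90 or ties it to the endpoint being analysed.

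**The concern.** Whether a Day-90 measurement was obtained per protocol is settled by Day 90. Attendance months later cannot change it. If later visits count, membership of the Day-90 set depends on events after the endpoint.

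That matters for two reasons. First, it discards valid data. Second, the selection may be related to outcome. At Day 90 subjects compare their own baseline and follow-up photographs for the SGAIS and the satisfaction questionnaire (Section 5.3), so they have a view of their result before deciding whether to return. In a non-inferiority trial the per-protocol analysis is read as a check on the ITT result, and such a check should not be defined by what subjects did afterwards.

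The wording also leaves room for two analysts to build different sets from the same sentence, with the choice possibly made after data have been seen.

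**Working it through.** **1. Windows with the 7-day tolerance** (synopsis and Table 3.1-1, plus Section 6.3)
- Day 90: 90±14 = 76 to 104; with 7 days, 69 to 111.
- Day 180: 180±21 = 159 to 201; with 7 days, 152 to 208.
- Day 365: 365±30 = 335 to 395; with 7 days, 328 to 402.

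Take a subject treated correctly, photographed on Day 90 and seen for the last visit on Day 405. Section 5.8 declares loss to follow-up six weeks after the last target, 365 + 42 = Day 407, so this subject is still in follow-up. But 405 exceeds 402. If the visit condition covers Day 365, the subject leaves the per-protocol analysis of the Day-90 endpoint.

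**2. The plan's own sample size** (Section 6.4.3.1: 73% in both arms, margin 15%, one-sided alpha 5%, power 80%, unpooled Z-test)
- n per arm = 2 × 0.73 × 0.27 × (1.645 + 0.842)² / 0.15² = 108.3, rounded up to 109.
- Total 218; 218 / (1 − 0.16) = 259.5, rounded up to 260.

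Both figures reproduce. The 109 refers to subjects with primary-endpoint data, not to the per-protocol set.

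**3. Effect of further loss on the supportive analysis.** Power = Φ(0.15 / √(2 × 0.73 × 0.27 / n) − 1.645). The loss rates below are assumptions; the documents give none.

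| Start per arm | Assumed loss | n per arm | Power |
|---|---|---|---|
| 109 | none | 109 | 80.2% |
| 109 | further 5% | 103.5 | 78.4% |
| 109 | further 10% | 98.1 | 76.5% |
| 109 | further 15% | 92.6 | 74.4% |
| 130 | 5% at Day 90 only | 123.5 | 84.4% |
| 130 | 5% at each of three visits, independent | 130 × 0.95³ = 111.5 | 81.0% |
| 130 | 10% at Day 90 only | 117.0 | 82.6% |
| 130 | 10% at each of three visits, independent | 130 × 0.90³ = 94.8 | 75.2% |

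Exact binomial power of the same test at n = 109, 98 and 93 is 80.5%, 76.9% and 74.9%, so the approximation is adequate.

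**4. Selection.** Suppose responders fail the later-visit condition with probability 10% and non-responders with 20% (assumed).
- Rate among those retained, from 73%: 0.73 × 0.90 / (0.73 × 0.90 + 0.27 × 0.80) = 0.657 / 0.873 = 75.3%, a shift of 2.3 points.
- In one arm only, the difference moves by 2.3 of the 15 margin points, in either direction depending on the arm.
- In both arms at 73%, both rates become 75.3% and the difference stays at zero.
- If the true rates sat at the margin, 73% and 58%, the same selection in both arms gives 75.3% and 0.58 × 0.90 / (0.58 × 0.90 + 0.42 × 0.80) = 60.8%, so a 15-point difference becomes about 14.4.

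**The case against.** The strongest reply is that the sentence is ambiguous and not a chosen rule. The list describes subjects in the plural, so a plural for their visits does not show that each subject needs all three; neither all nor each appears. The condition can also be read as a timing test for visits that took place, in which case a missed visit excludes nobody. The neighbouring condition on primary-endpoint data points towards Day 90. This stands in part: exclusion for a late visit follows from the literal text, exclusion for a missed one is only arguable, and the sponsor may have meant the relevant visit. It does not remove the point, because no section says so and the data condition is additional to the visit condition.

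The second reply is that little depends on it. Success rests on the primary efficacy objective (Section 6.2), tested on observed ITT data, and the plan sets no power target for the per-protocol set. This stands in full.

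The third is that starting from 109 and removing more assumes the whole 16% attrition is already spent by Day 90. With 5% per visit from 130 there is no shortfall against 80%. This also stands, which is why both starting points are shown.

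A reader might also infer that the rule delays a Day-90 result until the last Day-365 visit. The documents schedule no Day-90 readout, so that inference has no support.

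**Conclusion.** The visit condition should be tied to a time point. As written it permits, and read literally requires, a Day-90 analysis set that depends on attendance up to a year after treatment. The defect is confined to the supportive per-protocol analysis.

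The cost in precision is modest and rests on assumed miss rates: about 78% to 75% power after a further 5% to 15% loss from 109 per arm, and 81% with about 111 per arm under 5% loss per visit from 130.

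Two stronger readings should be resisted. One is that the trial's conclusion is at risk or the sample size wrong; neither follows, since the primary analysis does not use this set and the sample size reproduces. The other is that the per-protocol difference is biased by some 2.3 points. That figure needs outcome-related attendance in one arm only. Subjects are blinded to group (Section 5.4) and both arms follow the same visit schedule, so the documents give no evidence of it. At the planned equal rates, equal selection in both arms leaves the difference unchanged; with true rates at the margin, it would move it by about half a point under the same assumed attendance rates.

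**What to change.** Reword the visit condition in Section 6.3 along these lines: *attended the clinic visit for the time point being analysed, inside its window or no more than 7 days either side of it*. For the primary endpoint that is Days 69 to 111. Day-180 and Day-365 attendance then plays no part in the Day-90 per-protocol set.

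The change is one sentence, made before the data are seen. It needs no new data and alters no study procedure. It also matches Section 6.4.3.2, which already selects ITT subjects by whether they have data at the time point concerned. The one small downside is that per-protocol membership will vary by time point if the secondary outcomes are also run per protocol, so each table should state its own denominator.
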